## **8. STATISTICAL CONSIDERATIONS**

### **8.1 Endpoints**

#### **8.1.1 Primary Endpoint(s)**

##### **8.1.1.1 Primary Safety Endpoint(s)**

The frequency and percentage of subjects with solicited local and systemic AEs from vaccination to day 7 in study V98\_06E1. Time intervals after vaccination that will be summarized are: the first 30 minutes after vaccination, days 1-3 (excluding the first 30 min), days 4-7 and days 1-7 (excluding the first 30 min)..

The frequency and percentage of subjects with any unsolicited AEs from the day of vaccination (day 1 in study V98\_06E1) to day 31.

The frequency and percentage of subjects with SAEs, medically attended AEs, and AEs leading to study withdrawal from vaccination in study V98\_06E1 to day 181.

##### **8.1.1.2 Primary Efficacy Endpoint(s)**

This study has no efficacy endpoints.

##### **8.1.1.3 Primary Immunogenicity Endpoint(s)**

The primary immunogenicity endpoints are the percentages of subjects who reach pre-defined sequential serotype-specific (Ia, Ib and III) serum antibody levels at day 61 post vaccination, as measured by ELISA.

#### **8.1.2 Secondary Endpoint(s)**

##### **8.1.2.1 Secondary Safety Endpoint(s)**

This study has no secondary safety endpoints.

##### **8.1.2.2 Secondary Efficacy Endpoint(s)**

This study has no efficacy endpoints.

### **8.1.2.3 Secondary Immunogenicity Endpoint(s)**

The secondary immunogenicity endpoints are:

The percentage of subjects reaching pre-defined sequential serotype-specific (Ia, Ib and III) serum antibody levels as measured by ELISA at other time points and in subgroups of subjects defined by their pre-vaccination serotype-specific GBS antibody LLQ status in the V98\_06 study (or the V98\_06E1 study for the naive group).

The serotype-specific (Ia, Ib, and III) geometric mean concentrations (GMCs) as measured by ELISA at days 31 and 61 post-vaccination in study V98\_06E1 and in the subgroups of subjects defined according to their pre-vaccination serotype-specific GBS antibody LLQ status in the V98\_06 study (or V98\_06E1 study for the naive group).

The within subject geometric mean ratio (GMR) of serotype-specific (Ia, Ib & III) serum antibody levels as measured by ELISA at day 31 and 61. The GMRs will be determined relative to pre-vaccination in V98\_06E1 and separately relative to pre-vaccination in V98\_06 for all groups except the naive group. The GMRs will also be determined for subgroups of subjects defined according to their pre-vaccination serotype-specific GBS antibody LLQ status in the V98\_06 study or V98\_06E1 study for the naive group.

Reverse cumulative distribution function (RCDF) curves of serotype-specific (Ia, Ib and III) serum antibody levels, as measured by ELISA, at pre-vaccination in V98\_06 study or V98\_06E1 study for the naive group, vaccination, day 31 and day 61 post-vaccination in all subjects and by pre-vaccination serotype-specific GBS antibody LLQ status in the V98\_06 study or V98\_06E1 study for the naive group.

The anti-diphtheria geometric mean antibody concentrations measured by ELISA for samples collected before the first vaccination with GBS Trivalent Vaccine in the V98\_06 study or V98\_06E1 study for the naive group and on day 61 post-vaccination in V98\_06E1.

### **8.1.3 Exploratory Endpoint(s)**

#### **8.1.3.1 Exploratory Safety Endpoint(s)**

This study has no exploratory safety endpoints.

#### **8.1.3.2 Exploratory Efficacy Endpoint(s)**

This study has no efficacy endpoints.

### **8.1.3.3 Exploratory Immunogenicity Endpoint(s)**

The exploratory immunogenicity endpoints are:

The serotype-specific (Ia, Ib, and III) geometric mean titer (GMT) as measured by OPK at day 1 pre-vaccination and at days 31 and 61 post-vaccination in study V98\_06E1 in study subjects and in subgroups of subjects defined by pre-vaccination ELISA serotype-specific GBS antibody LLQ status in the V98\_06 study or V98\_06E1 study for the naive group.

The within subject GMR of serotype-specific (Ia, Ib & III) serum titers as measured by OPK at day 31 and 61. The GMRs will be determined relative to pre-vaccination in V98\_06E1. The GMRs will also be determined for subgroups of subjects defined according to their pre-vaccination ELISA serotype-specific GBS antibody LLQ status in the V98\_06 study, or V98\_06E1 study for the naive group.

Exploratory OPK objectives will be addressed in a randomly selected subset of up to 60 subjects (10 subjects per arm).

## **8.2 Success Criteria**

There is no pre-defined success criterion for this study.

### **8.2.1 Success Criteria for Primary Objective(s)**

#### **8.2.1.1 Success Criteria for Primary Safety Objective(s)**

There is no pre-defined success criterion for this study.

#### **8.2.1.2 Success Criteria for Primary Efficacy Objective(s)**

There is no pre-defined success criterion for this study.

#### **8.2.1.3 Success Criteria for Primary Immunogenicity Objective(s)**

There is no pre-defined success criterion for this study.

### **8.2.2 Success Criteria for Secondary Objective(s)**

There is no pre-defined success criterion for this study.

#### **8.2.2.1 Success Criteria for Secondary Safety Objective(s)**

There is no pre-defined success criterion for this study.

### **8.2.2.2 Success Criteria for Secondary Efficacy Objective(s)**

There is no pre-defined success criterion for this study.

### **8.2.2.3 Success Criteria for Secondary Immunogenicity Objective(s)**

There is no pre-defined success criterion for this study.

## **8.3 Analysis Sets**

The analysis sets described below are specific to study V98\_06E1. Similar analysis sets have already been defined in study V98\_06 for subjects receiving a second vaccination in this study.

### **8.3.1 All Enrolled Set**

All screened subjects who provide informed consent and provide demographic and/or baseline screening assessments, regardless of the subject's treatment status in this study.

### **8.3.2 All Exposed Set**

All subjects in the enrolled set who receive a study vaccination in study V98\_06E1.

### **8.3.3 Safety Set**

#### **Solicited Safety Set (solicited local and systemic adverse events and other solicited adverse events)**

All subjects in the Exposed Set with any solicited adverse event data and/or indicators of solicited adverse events (e.g., use of analgesics/antipyretics) reported in this study.

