**Table 3 Time and Events Table**

Events	Visit Type	Clinic Visit	Clinic Visit	Subject Diary Reminder Call	Safety Follow-up Call	Clinic Visit	Clinic Visit	Safety Follow-up Call	Safety Follow-up Call
	Day		1	3, 5	15	31	61	121	181
	Visit Window (Days)	-5 to 1	n/a	(-1/+1)/(-1/+2)	-3 to +3	-7 to +7	-7 to +7	-14 to +14	-14 to +14
	Visit Number	Pre-vaccination	1		2	3	4	5	6
Study Event	References								
Screening									
Informed Consent a	Section 5.1.1	X							
Medical History	Section 5.1.2	X	X b						
Physical Exam	Sections 5.1.2 and 5.3.1		X b						
Pregnancy Test c	Sections 3.5 and 5.1.2		X b						
Exclusion/Inclusion Criteria	Section 4	X	X b						
30 Minutes Post Injection Assessment	Section 5.2.1		X						
Subject Diary Dispensed with Training	Section 5.2.1		X						
Immunogenicity									

Events	Visit Type	Clinic Visit	Clinic Visit	Subject Diary Reminder Call	Safety Follow-up Call	Clinic Visit	Clinic Visit	Safety Follow-up Call	Safety Follow-up Call
	Day		1	3, 5	15	31	61	121	181
	Visit Window (Days)	-5 to 1	n/a	(-1/+1)/(-1/+2)	-3 to +3	-7 to +7	-7 to +7	-14 to +14	-14 to +14
	Visit Number	Pre-vaccination	1		2	3	4	5	6
Study Event	References								
Serology Blood Draw	Section 3.5		X b			X	X		
Study Treatment									
Vaccination	Section 5.2		X						
Safety									
Subject Diary Reminder Call	Section 5.2.2			X					
Symptom Directed Physical Exam	Sections 5.1.2 and 5.3.1					X	X		
Subject Diary Reviewed and Collected	Section 5.3.1					X			
Assess all AEs	Section 7.1		X		X	X			
Assess SAEs	Section 7.1.4		X		X	X	X	X	X
Assess for medically attended AEs and AEs leading to withdrawal	Sections 7.1.4.1 and 7.1.3		X		X	X	X	X	X

Events	Visit Type	Clinic Visit	Clinic Visit	Subject Diary Reminder Call	Safety Follow-up Call	Clinic Visit	Clinic Visit	Safety Follow-up Call	Safety Follow-up Call
	Day		1	3, 5	15	31	61	121	181
	Visit Window (Days)	-5 to 1	n/a	(-1/+1)/(-1/+2)	-3 to +3	-7 to +7	-7 to +7	-14 to +14	-14 to +14
	Visit Number	Pre-vaccination	1		2	3	4	5	6
Study Event	References								
Assess relevant medications	Sections 5.1.2 and 6.5	X	X		X	X	X	X	X

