#### **Subject Diary**

Paper Diaries (pDiaries) hereafter referred to as Subject Diaries will be the only source document allowed for solicited local and systemic adverse events (including body temperature measurements (preferably orally)), starting after the initial 30 minute post-vaccination period at the clinic. The following additional rules apply to documentation of safety information collected in the Subject Diary.

1. No corrections or additions to the information recorded by the subject within the Subject Diary will be allowed after it is delivered to the site.
2. Any blank or illegible fields on the Subject Diary must be described as missing in the CRF.

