#### **Case Report Forms**

This study utilizes Case Report Forms (CRFs) to collect study-related data from each subject. A qualified site staff member(s) is required to enter subject data in the CRFs in English based on the medical information available in each subject's source record.

Data should be entered into the CRF in a timely fashion following each subject's clinic visit, study procedure, or phone call. Each subject's CRF casebook will be compared with the subject's source records by a GSK-approved study monitor (or designee) over the duration of the study in order to ensure data collection accuracy.

The following additional rules apply to documentation of Subject Diary information collected in the CRFs:

1. The site must enter all readable entries in the Subject Diary into the CRF, including those values that may be biologically implausible (e.g. body temperature: 400°C).
2. Any illegible or implausible data should be reviewed with the subject. If an underlying solicited or unsolicited adverse event is described on review with the

subject, this should be described in the source document and reported as an unsolicited adverse event in the Adverse Event CRF (e.g., if the subject above confirms body temperature of 40°C on the day in which body temperature: 40°C was written into her Subject Diary, this fever of 40°C should be recorded in the Adverse Event CRF).

3. Any newly described safety information (including a solicited adverse event) must not be written into the Subject Diary and must be described in the study file as a verbally reported adverse event. Any adverse event reported in this fashion must be described as an unsolicited adverse event and therefore entered on the Adverse Event CRF.

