### **5.2.1 Post-vaccination Procedures**

The following post-vaccination procedures will be performed on day 1.

After vaccination, the subject will be observed for at least 30 minutes including observation for unsolicited adverse events, solicited adverse events, and body temperature measurement. Record all safety data collected during this time in the subject's source document.

A Subject Diary will be used in this study to document solicited adverse events. The Subject Diary is the only source for collection of these data; therefore, it is critical that the subject completes the Subject Diary correctly. The subject should be trained on how and when to complete each field of the Subject Diary.

The subject should be trained on how to self-measure local solicited adverse events and body temperature (preferably orally). The measurement of solicited local adverse events is to be performed using the ruler provided by the site.

The subject should be instructed how to perform body temperature measurement using the thermometer provided by the site. If the subject feels unusually hot or cold during the day, the subject should check body temperature. If the subject has fever, the highest body temperature observed that day should be recorded in the Subject Diary.

Subject Diary training should be directed at the individual(s) who will perform the measurements of adverse events and who will enter the information into the Subject Diary. This individual may not be the subject, but if a person other than the subject enters information into the Subject Diary, this person's identity must be documented in the

Subject Diary and/or subject's source record. Any individual that makes entries into the Subject Diary must receive training on completion of the Subject Diary at the time of the visit. This training must be documented in the subject's source record.

The same individual should complete the Subject Diary throughout the course of the study.

The site should schedule the subject diary reminder calls and the next study safety follow-up call with the subject.

The subject should be reminded of the next planned study activity. The subject will be reminded to complete the Subject Diary and to contact the site if there are any questions, and to contact the site immediately (or as soon as the subject is medically stable) if the subject has a medical condition that leads to a hospitalization or an emergency room visit or to a visit to/by a doctor or is of concern.

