#### **Unsolicited Safety Set (unsolicited adverse events)**

All subjects in the Exposed Set with unsolicited adverse event data reported in this study.

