##### **8.4.2.1.2 Analysis of Solicited Local, Systemic and Other Adverse Events**

All solicited adverse events will be summarized according to defined severity grading scales. Use of medication to prevent/treat fever will be summarized according to frequencies and percentages reporting “Yes” and “No”.

Frequencies and percentages of subjects experiencing each adverse event will be presented for each symptom severity. Summary tables showing the occurrence of any local or systemic adverse event overall and at each time point will also be presented.

Post-vaccination solicited adverse events reported from day 1 to day 7 will be summarized for the intervals day 1-3, day 4-7, day 1-7 by maximal severity and by vaccine group, excluding the 30 minute measurement, which will be summarized separately. The severity of solicited local adverse events, including injection-site erythema, swelling and induration will be summarized according to categories based on linear measurement: 0 mm, <25 mm, 25 to 50 mm, 51-100 mm, > 100 mm.

Injection site pain/tenderness and systemic adverse events (except fever) occurring up to day 7 after each vaccination will be summarized according to “mild”, “moderate” or “severe”.

Each solicited local and systemic adverse event will also be further summarized as “none” versus “any”.

Implausible measurements (for further definition see statistical analysis plan) will be left out of the analysis.

Use of antipyretics and analgesics will be summarized by frequency, by type of use (prophylactic versus treatment), and percentage of subjects reporting use.

Body temperature will be summarized by 0.5 °C and 1.0 °C increments from 36.0 °C up to  $\geq 40$  °C and will be broken down according by route of measurement.

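### Do the safety set definitions in section 8.3.3 leave the primary safety percentages without a sound denominator?

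*Combined protocol and SAP*

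**What the plan says.** Section 8.3.3 defines three safety sets.

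- The Solicited Safety Set is "All subjects in the Exposed Set with any solicited adverse event data and/or indicators of solicited adverse events" reported in the study.
- The Unsolicited Safety Set is "All subjects in the Exposed Set with unsolicited adverse event data reported in this study".
- The Overall Safety Set is the union of the two.

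Solicited data come from two sources. Under section 5.2.1, after vaccination "the subject will be observed for at least 30 minutes including observation for unsolicited adverse events, solicited adverse events, and body temperature measurement". From the end of that period, section 3.4.2 provides that "Subject Diaries will be the only source document allowed for solicited local and systemic adverse events", and that blank or illegible diary fields are entered in the CRF as missing. Table 3 places the event "Subject Diary Reviewed and Collected" at the day 31 visit only, with a window of 7 days either side. A reaction that the subject describes later may not be written into the diary; under section 3.4.2, "Any adverse event reported in this fashion must be described as an unsolicited adverse event".

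The primary safety endpoints in section 8.1.1.1 are frequencies and percentages of subjects. For solicited events the intervals are the first 30 minutes, days 1-3, days 4-7 and days 1-7. Section 8.4.2.1.2 gives the day-interval summaries by vaccine group, "excluding the 30 minute measurement, which will be summarized separately". Neither that section nor 8.4.2.1.3 on unsolicited events states a denominator. The synopsis refers only to the appropriate safety sets.

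**The concern.** A set entered on any solicited data contains subjects with no data at all for the diary intervals. Used as the divisor, it would count a subject without a diary as having had no reaction. Reported day 1-7 reactogenicity after the second dose would then be too low, and by different amounts in groups that differ in diary return. A reaction told to staff by a subject who lost her diary would move to the unsolicited table and could not repair the solicited one.

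The unsolicited definition also looks loose. If only a reported event counts as data, everyone in the set has an event and the percentage says nothing. If a recorded absence of events counts as data, the set is close to the All Exposed Set.

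These percentages are the primary safety result, in groups of at most 40 (20 in the naive group), so their denominators should be clear.

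**Working it through.** The plan states no safety denominator, event rate or diary non-return rate, so there is no figure to reproduce. The check has two parts: the size of the effect under assumed rates, and whether the text leads to the harmful reading.

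**Size under assumed rates.** Inputs: groups of up to 40 and a naive group of 20 (Table 3-1). Assumed: a true diary reaction rate of 30% or 60%, and a share *m* of subjects without a diary of 5%, 10% or 20%, with diary loss unrelated to reactions.

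Reported rate = true rate × (1 − *m*):

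| *m* | In a group of 40 | True 60% | True 30% |
|---|---|---|---|
| 5% | 2 | 57% | 28.5% |
| 10% | 4 | 54% | 27% |
| 20% | 8 | 48% | 24% |

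Whole subjects at a rate near 60% in a group of 40 give the same picture:

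- 2 diaries missing: 23/40 = 57.5% against 23/38 = 60.5%
- 4 missing: 22/40 = 55.0% against 22/36 = 61.1%
- 8 missing: 19/40 = 47.5% against 19/32 = 59.4%

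Unequal return: with 2 of 20 naive diaries missing and none of 40 elsewhere, an equal 60% would show as 0.60 × 18/20 = 54% against 60%, a gap of 6 points. For scale, the exact 95% interval for 12/20 is 36.1% to 80.9%, and for 24/40 it is 43.3% to 75.1%. With *m* = 0 the effect is zero.

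Timing of collection: day 31 ± 7 is days 24 to 38, which is 17 to 31 days after the last diary day (24 − 7 and 38 − 7). Some loss is plausible.

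**Does the text lead to the harmful reading?**

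1. Section 3.4.2 codes blank diary fields as missing. Section 8.4.2.1.2 leaves implausible measurements out of the analysis. Both point to unusable data being dropped, not scored as no reaction.
2. Section 7.1.1 grades pain, warmth and the systemic events on scales that include *none*. Section 8.4.2.1.2 has a 0 mm category and a none-versus-any summary. *None* is therefore a value that someone recorded, and a missing diary supplies no such value.
3. The same usage settles the unsolicited set. If a recorded absence is data, a subject interviewed at day 15 and day 31 with nothing to report has data and belongs to the set. The events-only reading, under which an assumed 40% becomes 0.4N/0.4N = 100%, makes the endpoint meaningless, and no analyst would use it.
4. The two worries need opposite readings of similar wording. The solicited worry needs an uneventful 30-minute check to count as data. The unsolicited worry needs an uneventful interview not to count. Under either reading applied consistently, one of them largely disappears.
5. The set titles say which events they serve. Section 8.4.2.1.3, on unsolicited events, contains the summaries of SAEs, withdrawals and medically attended events. The link from set to table is implicit but easy to follow.

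**The case for a change.** The strongest case for a change is that the protocol names its sets elsewhere: the Enrolled Set for exposure (8.4.2.1.1), the per-protocol and full analysis sets for primary immunogenicity (8.4.2.3.2), and the per-protocol set for secondary immunogenicity (8.4.3.3.2). The two safety sections name none. The missing-data paragraph in 8.4.3.3.3 covers immunogenicity only. What the protocol expressly defers to a statistical analysis plan is exclusionary deviations (8.3.8) and implausible values (8.4.2.1.2), not denominators. Early termination may be handled by telephone (5.5.1), with no diary handed over. Three sentences would settle the matter at no cost to conduct.

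Much of this stands as description. The denominator for the diary intervals is not written down, and the wording of the solicited set does not supply it. The claim that the plan therefore produces wrong percentages does not stand, because no instruction makes the whole set the divisor.

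The protocol also works against diary loss. Investigators must judge that the subject will complete the diary (footnote to 4.1), subjects are trained (5.2.1), and reminder calls are made on days 3 and 5 (5.2.2). A reaction reported verbally still enters the unsolicited endpoint.

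The natural replacement rules are also conventions with their own weaknesses. Dividing all events to day 181 by the All Exposed Set counts subjects lost to follow-up as event-free, the same dilution that was objected to for diaries. Requiring one diary entry per interval treats a mostly blank diary as complete.

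**Conclusion.** The concern describes a real silence in the text but does not call for a change to the plan. One Solicited Safety Set can include subjects without diary data, and no denominator is stated for days 1-3, 4-7 and 1-7. Analysts ordinarily use the subjects with non-missing data in each interval and show how many have none, and that agrees with how the protocol treats missing fields and recorded absences. The unsolicited set, read the same way, includes subjects who were assessed and had no event.

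Under the unfavourable reading, the loss would be 3 to 12 points at an assumed 60% reaction rate, or 1.5 to 6 points at 30%, for 5% to 20% of diaries missing. None of these rates comes from the documents. Nothing downstream depends on the choice: section 8.2 sets no success criterion, the study is declared exploratory, and the safety sections plan no between-group differences or intervals. The conclusion rests on the tables following the usual non-missing convention; a reader can confirm that from the denominators printed in them.

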#### **Unsolicited Safety Set (unsolicited adverse events)**

All subjects in the Exposed Set with unsolicited adverse event data reported in this study.

#### **Overall Safety Set**

All subjects who are in the Solicited Safety Set and/or Unsolicited Safety Set.

Subjects will be analyzed as "treated" (i.e., according to the vaccine a subject received).

